Appendix 3 **Criteria for Identifying ECG Measurements of Potential Clinical Relevance**

Variable	Criterion Value ^a	Change Relative to Baseline ^a
Heart Rate	≥ 120 bpm ≤ 50 bpm	increase of ≥ 15 bpm decrease of ≥ 15 bpm
PR	≥ 200 msec	increase of ≥ 50 msec
QRS	≥ 120 msec	increase of ≥ 20 msec
QTcF	> 450 msec (males) > 470 msec (females)	

^aIn order to be identified as potentially clinically relevant, an on-treatment value must meet the “Criterion Value” and also represent a change from the subject’s baseline value of at least the magnitude shown in the “Change Relative to Baseline” column.

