3.4.3 Exclusion Criteria

Subjects will be excluded if they fall under any of the exclusion criteria described in Table 3.4.3-1.

Table 3.4.3-1 Exclusion Criteria	
1	Patients who experienced SAEs that were judged to be related to the IMP by the investigator or subinvestigator in Trial 331-102-00088.
2	Patients who experienced episodes of delirium during Trial 331-102-00088.
3	Patients who had clinically significant nervous, hepatic, renal, metabolic, immunological, hematological, cardiovascular, pulmonary, or digestive abnormalities during Trial 331-102-00088.
4	Patients with psychological symptoms or behavioral problems clearly due to other diseases or a drug substance.
5	Patients who had a stroke, transient ischemic attack, or pulmonary embolism during Trial 331-102-00088.
6	Patients who had heart failure of New York Heart Association Class III or higher during Trial 331-102-00088.
7	Patients who received pharmacological therapy for arrhythmia or ischemic heart disease during Trial 331-102-00088, not including patients for whom the investigator or subinvestigator judges pharmacological therapy to be the primary prevention of ischemic heart disease.
8	Patients whose QTcF values (based on central laboratory or mechanical reading) at Week 10 of Trial 331-102-00088 meet the criteria below. If mechanically read QTcF values meet the criteria, 2 ECG examinations should be additionally performed, and at least 1 of these 2 measurements must meet the criteria. 
 Men: ≥ 450 msec; women: ≥ 470 msec
9	Patients with the following abnormal laboratory test values at Week 10 of Trial 331-102-00088 (assessed on the basis of the results from the central or local laboratory): 
 Platelet count: $\leq 75,000/\text{mm}^3$ Hemoglobin: $\leq 9 \text{ g/dL}$ Neutrophil count: $\leq 1000/\text{mm}^3$ Aspartate aminotransferase (AST) and alanine aminotransferase (ALT): > 2 times the upper limit of normal (ULN) Creatine phosphokinase (CPK): > 3 times ULN (however, this does not apply if the medical monitor judges that there will be no medically significant problems) Albumin: $< 3 \text{ g/dL}$
10	Patients who required insulin treatment during Trial 331-102-00088.

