3.9.3.2 Documenting Reasons for Discontinuation

All subjects have the right to withdraw, and the investigator or subinvestigator can discontinue a subject's participation in the trial at any time if medically necessary. In

addition, subjects meeting the following criteria must be withdrawn from the trial. Only one main reason for discontinuation will be recorded in the CRF.

- Adverse event
 - Death
 - Continuation of IMP would place the subject at undue risk, as determined by the investigator or subinvestigator (eg, there is a safety concern possibly, probably, or likely related to IMP).
 - SAE
 - The dose of brexpiprazole needs to be reduced to lower than 1 mg due to the occurrence of an AE.
 - The subject experiences worsening of agitation, and the investigator or subinvestigator judges that the subject should be withdrawn from the trial (worsening of agitation is to be reported as an AE).
 - The subject decides to discontinue the treatment because of annoyance or discomfort due to a nonserious AE that is not otherwise determined to be an undue hazard.
- Subjects becoming bedridden and requiring assistance for excretion, eating, and changing clothes
- Subject's withdrawal of informed consent
- Legally acceptable representative's withdrawal of informed consent
- Caregiver's withdrawal of informed consent
- Marked noncompliance with the IMP regimen (compliance rate of < 65% during the interval between the previous date of compliance verification and the current date of compliance verification)
- Protocol deviation (other than marked noncompliance with the IMP regimen)
 - The subject is discovered to have not met the inclusion/exclusion criteria.
 - The subject has received any prohibited concomitant drugs or is judged to be in need of prohibited drugs.
- Lost to follow-up
- Lack of efficacy
- Pregnancy (see [Section 5.5 Pregnancy](#))
- Termination of all or part of the trial by the sponsor
- Investigator or subinvestigator's judgment (for reasons other than occurrence of AE)
- Other
 - After initiation of IMP treatment, any of the following external test results at Week 10 of Trial 331-102-00088 are obtained:
 - QTcF on the basis of ECG results from the central ECG laboratory is ≥ 450 msec in men or ≥ 470 msec in women (in triplicate ECG examinations, at least 2 measurements meet the criteria).

- Results from the central laboratory:
 - Platelet count: $\leq 75,000/\text{mm}^3$
 - Hemoglobin: $\leq 9 \text{ g/dL}$

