9.6 Electrocardiogram Data

For heart rate, PR interval, RR interval, QRS interval, QT interval, and QT corrected for heart rate (QTc), descriptive statistics of actual measurements and changes from baseline at each time point and the final assessment (Week 14 LOCF) will be calculated.

A shift table from baseline for normal/abnormal 12-lead electrocardiogram (ECG) (evaluated at the trial site) will be produced.

Numbers and proportions of subjects with actual measurements of QTc [QTcF, QTcB, QTcN = QT interval/(RR interval)^{0.37}] not meeting the criteria of > 450 msec, > 480 msec, or > 500 msec at baseline and meeting the criteria after treatment will be determined. Numbers and proportions of subjects with changes from baseline of > 30 msec and > 60 msec will be determined. Numbers and proportions of subjects with actual measurements of > 450 msec with a % change from baseline of > 10% will be determined.

Numbers and proportions of subjects with ECG results meeting the criteria for potentially clinically significant ECG data (Appendix 3) will be determined. A listing of these subjects will be provided.

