9.7.3 S-STS

For the score for each S-STS item (2 through 14), total score, suicidal ideation subscale score, and suicidal behavior subscale score, descriptive statistics of actual measurements

and changes from baseline at each time point and the final assessment (Week 14 LOCF) will be calculated.

10 Pharmacokinetic Analyses

Not applicable.

11 Pharmacodynamic Analyses

Not applicable.

12 Pharmacogenomic Analyses

Not applicable.

13 Analysis of Other Endpoints

Analysis of other endpoints will be performed using the safety analysis set. Baseline is defined as the last data obtained prior to initiation of IMP treatment.

- ADCS-ADL
- MMSE

For ADCS-ADL total score and MMSE total score, descriptive statistics of actual measurements and changes from baseline at each time point and the final assessment (Week 14 LOCF) will be calculated.

14 Interim Analysis

In this trial, safety will also be evaluated by the IDMC, when approximately 25%, 50%, and 75% of the target number of subjects in the preceding Trial 331-102-00088 have completed or discontinued the trial. Additional evaluation by the IDMC may be performed depending on the status of subject enrollment into the current trial (331-102-00184).

A statistical analysis plan for interim analysis is described in a separate interim analysis plan.

15 Changes in the Planned Analyses

[REDACTED]

The following changes were made to categorical analyses of QTc:

- Only subjects with postdose QTc meeting the criteria will be summarized, instead of summarization at all time points.
- Only subjects with QTc not meeting the criteria at baseline and meeting the criteria after baseline will be summarized.

16 References

Not applicable.

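### The QTcF count in CT-12.4 has no not-met-at-baseline condition, so the few subjects found after dosing to have been over the limit at baseline can be counted as on-treatment abnormalities

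*SAP*

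**What the plan says.** - SAP Appendix 3, QTcF row: the criterion is "QTcF > 450 msec (males) > 470 msec (females", and the change cell is empty. The footnote says "an on-treatment value must meet the “Criterion Value” and also represent a change from the subject’s baseline value of at least the magnitude shown". Heart rate, PR and QRS each give a magnitude.
- SAP 9.6 applies the appendix: "Numbers and proportions of subjects with ECG results meeting the criteria for potentially clinically significant ECG data (Appendix 3) will be determined". By their titles in SAP Appendix 4, the outputs are CT-12.4 (incidence) and CT-12.5 (listing).
- SAP 9.6 also plans QTc categories of 450, 480 and 500 msec (CT-12.3), counted only if not met at baseline. SAP 15 repeats this for categorical QTc analyses: "Only subjects with QTc not meeting the criteria at baseline and meeting the criteria after baseline will be summarized". SAP 9.3 sets the same rule for the Appendix 2 laboratory criteria.
- Protocol 3.4.3, criterion 8, excludes subjects by Week 10 QTcF: "Men: ≥ 450 msec; women: ≥ 470 msec". The reading may be central or mechanical. Table 3.8-1 makes that Week 10 visit the baseline of this trial.
- Protocol 3.9.3.2 requires withdrawal when "After initiation of IMP treatment, any of the following external test results at Week 10 of Trial 331-102-00088 are obtained", and lists a central QTcF at or above the same limits.

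**The concern.** QTcF is the only criterion in SAP Appendices 1 to 3 with neither safeguard. All Appendix 1 rows and the other Appendix 3 rows need a change from baseline. Appendix 2 is mostly level-only, but SAP 9.3 restricts it to subjects who did not meet the criterion at baseline. A QTcF over the limit both before the first dose and after it therefore satisfies the CT-12.4 rule, although nothing changed on treatment. Protocol 6.6.4 describes this analysis as one of clinically significant changes in ECG parameters.

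The trial is uncontrolled and safety is its objective, so a reader of CT-12.4 has no comparison arm against which to discount such a case. CT-12.3 and CT-12.4 could also disagree on the same man at the same 450 msec limit, with no stated reason.

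**Working it through.** The plan gives no figure to reproduce here. The check sets the rules side by side, follows the route by which a subject can be counted, and then estimates its size.

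**1. Rules compared**

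| Criterion | Change required | Not met at baseline required |
|---|---|---|
| Appendix 1 (vital signs, weight) | yes, every row | no |
| Appendix 2 (laboratory) | a few rows | yes (SAP 9.3) |
| Appendix 3: heart rate, PR, QRS | yes | no |
| QTc > 450, > 480, > 500 (CT-12.3) | no | yes (SAP 9.6, 15) |
| Appendix 3: QTcF (CT-12.4) | none shown | no |

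**2. Entry on a central reading**

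Baseline is below 450 (men) or 470 (women). A later value above 450 or 470 is then always a new crossing. The missing condition changes nothing for these subjects.

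**3. Entry on a mechanical reading**

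- The central result can arrive after dosing and be at or above the limit. The subject is withdrawn (Protocol 3.9.3.2) but has had at least one dose, so remains in the safety set (SAP 5.2).
- Protocol 3.8.1.5 asks for a prompt examination at discontinuation using the Table 3.8-1 assessments. I take this to include an ECG; the table's last column header is lost in the text I have.
- SAP 3.4 drops only data from 7 days or later after the final dose, so a prompt ECG is analysed.
- With triplicate ECGs, withdrawal needs at least 2 of 3 central readings over the limit. A subject with one high reading stays on treatment, and that reading could be the baseline value.

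**4. Example: a man at 456, then 453**

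The change is 453 − 456 = −3 msec.
- CT-12.4 as written: 453 > 450, so he is counted.
- CT-12.3, > 450: already met at baseline, so not counted.
- Changes > 30 or > 60 msec: not counted.

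**5. Size**

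The documents give no QTcF means or variability, so every input except N = 157 is an assumption:
- mean 410 to 420 (men) and 420 to 430 (women); between-subject SD 15 to 20; within-subject SD 8 to 12; 60% women; no drug effect;
- four post-baseline ECGs (the marks in the ECG row of Table 3.8-1), or one if withdrawn;
- mechanical minus central difference with SD 0 (central entry), 6 or 12 msec, with everyone entering on mechanical readings in the last two cases.

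Results per 157 subjects, from 2,000,000 simulated subjects per setting:

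| Entry reading | Late central result, withdrawn | All QTcF flags | Flags with baseline over the limit |
|---|---|---|---|
| Central | 0 | 1.3 to 14.8 | 0 |
| Mechanical, SD 6 | 0.2 to 2.1 | 1.4 to 15.8 | 0.04 to 0.6 |
| Mechanical, SD 12 | 0.3 to 3.4 | 1.3 to 15.3 | 0.1 to 1.2 |

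The last column is what a not-met-at-baseline condition removes. Allowing for wider inputs, roughly 0 to 2 of 157 is a fair bracket.

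**6. Would a > 30 msec condition be better?**

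Take a woman going from 455 to 479: +24 msec, and 24/455 = 5.3%.
- CT-12.3: > 450 was met at baseline; > 480 is not reached.
- Changes > 30 msec, and > 450 with > 10% change: not met.
- Appendix 3: 479 > 470, so she is counted.

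More generally, take a baseline of 451 to 469 and a highest on-treatment value of 471 to 480. The rise is at most 480 − 451 = 29 msec, or 29/451 = 6.4%. Appendix 3 is then the only planned incidence count of QTcF that records the crossing. A > 30 msec condition would delete it; a baseline condition keeps it.

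**The case against.** **SAP 15 may already cover this.** It speaks of categorical QTc analyses in general, and CT-12.4 could be read as one of them. That is plausible. But SAP 9.6 writes the condition into the 450/480/500 sentence and leaves it out of the Appendix 3 sentence, so a programmer could apply either rule.

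**The shared cut-off prevents the problem.** For central-reading entry this is correct. A reader might infer from the missing condition that CT-12.4 widely counts prolongation present before dosing. The documents do not support that, because criterion 8 is applied at the baseline visit itself. Only late central results, a single high reading among triplicates, and eligibility deviations remain.

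**A reader might also infer that CT-12.4 is mostly noise, because enrolment is cut off at the limit it then counts.** Chance crossings do occur: step 5 gives about 1 to 16 flags per 157 with no drug effect. But this holds for any fixed limit, CT-12.3 included. For men entered below 450, the QTcF > 450 category and the Appendix 3 row count the same subjects. With assumed means of 415 and 425, SDs of 18 and 10 and four ECGs, both give 7.0% of men. In women the > 450 category gives 13.2% and Appendix 3 only 2.7%. Noise is no reason to single out this row.

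**The blank cell may simply mean that no change is required, or may be lost text.** Both are possible. Appendix 1 prints a dash in the unused cell of its weight row, so the blank still needs to be settled.

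**Conclusion.** The point stands as a narrow inconsistency of small effect. As written, the CT-12.4 rule can count a subject whose QTcF was over the limit before the first extension dose and did not rise. The plan's parallel rules for laboratory values and QTc categories would not count that subject.

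The number affected is zero if eligibility rested on central readings, and roughly 0 to 2 of 157 if all entered on mechanical readings. That range depends wholly on assumed means, SDs and reading differences. The documents do not say how many subjects entered by each route.

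The conclusion also assumes that the QTcF change cell is truly empty and that the discontinuation examination includes an ECG. All these tables are descriptive, and CT-12.3 and the change-from-baseline counts give a separate view of QTc. The overall QT assessment therefore does not depend on this row.

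**What to change.** 1. In SAP 9.6, count a subject's QTcF in CT-12.4 only if the sex-specific Appendix 3 criterion was not met at baseline and was met after treatment, in line with SAP 15.
2. In Appendix 3, put a dash in the QTcF change cell, as Appendix 1 does for an unused cell, so that the footnote clearly sets no magnitude for that row.
3. In CT-12.5, list every on-treatment QTcF above the limit and flag those that met the criterion at baseline.
4. Do not add a > 30 msec condition. SAP 9.6 already tabulates that change separately, and step 6 shows which women's crossings would be lost.

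The cost is a few lines of SAP text, one baseline filter and one listing flag, with no new data. No high value is hidden: the subjects removed from the count remain in the listing.

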Appendix 4 List of Summary Tables

- CT-8.2.1 Incidence of TEAEs by MedDRA System Organ Class and Preferred Term (Safety Analysis Set)
- CT-8.2.2 Incidence of Drug-related TEAEs by MedDRA System Organ Class and Preferred Term (Safety Analysis Set)
- CT-8.3.1 Incidence of TEAEs by MedDRA System Organ Class, Preferred Term and Severity (Safety Analysis Set)
- CT-8.3.2 Incidence of Drug-related TEAEs by MedDRA System Organ Class, Preferred Term and Severity (Safety Analysis Set)
- CT-8.4.1 Incidence of Deaths due to TEAEs by MedDRA System Organ Class and Preferred Term (Safety Analysis Set)
- CT-8.4.2 Incidence of Deaths due to Drug-related TEAEs by MedDRA System Organ Class and Preferred Term (Safety Analysis Set)
- CT-8.5.1 Incidence of Serious TEAEs by MedDRA System Organ Class and Preferred Term (Safety Analysis Set)
- CT-8.5.2 Incidence of Serious Drug-related TEAEs by MedDRA System Organ Class and Preferred Term (Safety Analysis Set)
- CT-8.6.1 Incidence of TEAEs Resulting in Discontinuation of IMP by MedDRA System Organ Class and Preferred Term (Safety Analysis Set)
- CT-8.6.2 Incidence of Drug-related TEAEs Resulting in Discontinuation of IMP by MedDRA System Organ Class and Preferred Term (Safety Analysis Set)
- CT-8.7.1 Incidence of TEAEs Resulting in Dose Reduction of IMP by MedDRA System Organ Class and Preferred Term (Safety Analysis Set)
- CT-8.7.2 Incidence of Drug-related TEAEs Resulting in Dose Reduction of IMP by MedDRA System Organ Class and Preferred Term (Safety Analysis Set)
- CT-8.8.1 Incidence of TEAEs of at Least 2% in Any Group by MedDRA System Organ Class and Preferred Term (Safety Analysis Set)
- CT-8.8.2 Incidence of Drug-related TEAEs of at Least 2% in Any Group by MedDRA System Organ Class and Preferred Term (Safety Analysis Set)
- CT-8.9.1 Incidence of TEAEs by MedDRA System Organ Class, Preferred Term and Time to First Onset (Safety Analysis Set)
- CT-8.9.2 Incidence of Drug-related TEAEs by MedDRA System Organ Class, Preferred Term and Time to First Onset (Safety Analysis Set)
- CT-8.10.1 Incidence of TEAEs for EPS (Safety Analysis Set)
- CT-8.10.2 Incidence of TEAEs for Accidents and Injuries Including Fall (Safety Analysis Set)
- CT-8.10.3 Incidence of TEAEs for Cerebrovascular Events (Safety Analysis Set)
- CT-8.10.4 Incidence of TEAEs for Cardiovascular Events (Safety Analysis Set)
- CT-8.10.5 Incidence of TEAEs for Effect on Glucose (Safety Analysis Set)
- CT-8.10.6 Incidence of TEAEs for Effect on Lipids (Safety Analysis Set)
- CT-8.10.7 Incidence of TEAEs for Effect on Weight (Safety Analysis Set)
- CT-8.10.8 Incidence of TEAEs for Haematopoietic/Leukopenia (Safety Analysis Set)
- CT-8.10.9 Incidence of TEAEs for Hypersensitivity (Safety Analysis Set)
- CT-8.10.10 Incidence of TEAEs for Neuroleptic Malignant Syndrome (Safety Analysis Set)
- CT-8.10.11 Incidence of TEAEs for Orthostatic Hypotension, Dizziness, and Syncope (Safety Analysis Set)
- CT-8.10.12 Incidence of TEAEs for Effect on Prolactin (Safety Analysis Set)
- CT-8.10.13 Incidence of TEAEs for QT Prolongation (Safety Analysis Set)
- CT-8.10.14 Incidence of TEAEs for Rhabdomyolysis and CPK Elevation (Safety Analysis Set)
- CT-8.10.15 Incidence of TEAEs for Seizures (Safety Analysis Set)
- CT-8.10.16 Incidence of TEAEs for Somnolence (Safety Analysis Set)
- CT-8.10.17 Incidence of TEAEs for Suicidality (Safety Analysis Set)
- CT-8.10.18 Incidence of TEAEs for VTE (Thrombotic and Embolic Events) (Safety Analysis Set)
- CT-8.10.19 Incidence of TEAEs for Infective Pneumonia (Safety Analysis Set)

- CT-8.11.1 Incidence of TEAEs by MedDRA System Organ Class and Preferred Term by Medical Care Category (Safety Analysis Set)
- CT-8.11.2 Incidence of TEAEs by MedDRA System Organ Class and Preferred Term by Prior Antipsychotics (Safety Analysis Set)
- CT-8.11.3 Incidence of TEAEs by MedDRA System Organ Class and Preferred Term by Main Care Giver (Safety Analysis Set)
- CT-8.11.4 Incidence of TEAEs by MedDRA System Organ Class and Preferred Term by Gender (Safety Analysis Set)
- CT-8.11.5.1 Incidence of TEAEs by MedDRA System Organ Class and Preferred Term by Age(< 80, >= 80) (Safety Analysis Set)
- CT-8.11.5.2 Incidence of TEAEs by MedDRA System Organ Class and Preferred Term by Age(<65, >=65 - <75, >=75) (Safety Analysis Set)
- CT-8.11.6 Incidence of TEAEs by MedDRA System Organ Class and Preferred Term by Baseline Weight (Safety Analysis Set)
- CT-8.11.7 Incidence of TEAEs by MedDRA System Organ Class and Preferred Term by Baseline BMI (Safety Analysis Set)
- CT-8.11.8 Incidence of TEAEs by MedDRA System Organ Class and Preferred Term by Impact of COVID-19 Pandemic (Safety Analysis Set)
- CT-8.11.9 Incidence of TEAEs by MedDRA System Organ Class and Preferred Term by Concomitant Antidementia Drugs (Safety Analysis Set)
- CT-9.1 Listing of Deaths (Safety Analysis Set)
- CT-9.2 Listing of Serious Adverse Events (Safety Analysis Set)
- CT-9.3 Listing of Discontinuation of IMP due to Adverse Events (Safety Analysis Set)
- CT-9.4 Listing of Dose Reduction due to Adverse Events (Safety Analysis Set)
- CT-10.1.1 Mean Change From Baseline in Clinical Laboratory Test Results - Serum Chemistry (Safety Analysis Set)
- CT-10.1.2 Mean Change From Baseline in Clinical Laboratory Test Results - Hematology (Safety Analysis Set)
- CT-10.1.3 Mean Change From Baseline in Clinical Laboratory Test Results - Urinalysis (Safety Analysis Set)
- CT-10.1.4 Mean Change From Baseline in Clinical Laboratory Test Results - Prolactin, by Gender (Safety Analysis Set)
- CT-10.1.5 Mean Change From Baseline in Clinical Laboratory Test Results - Other Tests (Safety Analysis Set)
- CT-10.2.1 Shift Tables of Clinical Laboratory Test Results - Serum Chemistry (Safety Analysis Set)
- CT-10.2.2 Shift Tables of Clinical Laboratory Test Results - Hematology (Safety Analysis Set)
- CT-10.2.3 Shift Tables of Clinical Laboratory Test Results - Urinalysis1 (Safety Analysis Set)
- CT-10.2.4 Shift Tables of Clinical Laboratory Test Results - Urinalysis2 (Safety Analysis Set)
- CT-10.2.5 Shift Tables of Clinical Laboratory Test Results - Prolactin, by Gender (Safety Analysis Set)
- CT-10.2.6 Shift Tables of Clinical Laboratory Test Results - Other Tests (Safety Analysis Set)
- CT-10.3.1 Incidence of Laboratory Test Values With Potential Clinical Relevance (Safety Analysis Set)
- CT-10.3.2 Listing of Laboratory Test Values With Potential Clinical Relevance by Subject (Safety Analysis Set)
- CT-10.4.1 Incidence of Potential Hy's Law Cases (Safety Analysis Set)
- CT-10.4.2 Listing of Potential Hy's Law Cases (Safety Analysis Set)
- CT-10.5.1 Incidence of Laboratory Test Values With Potential Clinical Relevance - Prolactin (Safety Analysis Set)
- CT-10.5.2 Listing of Laboratory Test Values With Potential Clinical Relevance - Prolactin (Safety Analysis Set)
- CT-10.6.1 Incidence of Treatment-emergent Significant Change in Lipids (Safety Analysis Set)
- CT-10.6.2 Listing of Treatment-emergent Significant Change in Lipids (Safety Analysis Set)

CT-10.7.1 Incidence of Treatment-emergent Significant Change in Glucose (Safety Analysis Set)
CT-10.7.2 Listing of Treatment-emergent Significant Change in Glucose (Safety Analysis Set)
CT-11.1 Mean Change From Baseline in Vital Signs (Safety Analysis Set)
CT-11.2 Incidence of Potentially Clinically Relevant Abnormalities in Vital Signs (Safety Analysis Set)
CT-11.3 Listing of Potentially Clinically Relevant Abnormalities in Vital Signs (Safety Analysis Set)
CT-11.4 Summary of Mean Change From Baseline by Study Week in Body Weight (kg) (Safety Analysis Set)
CT-11.5 Summary of Mean Change From Baseline by Study Week in BMI (kg/m²) (Safety Analysis Set)
CT-11.6 Incidence of Potentially Clinically Relevant Weight Gain or Loss by Baseline BMI (Safety Analysis Set)
CT-12.1 Mean Change From Baseline in ECG Results (Safety Analysis Set)
CT-12.2 Shift Tables of ECG (Safety Analysis Set)
CT-12.3 Incidence of Categorical Increases in QT Evaluations (Safety Analysis Set)
CT-12.4 Incidence of Potentially Clinically Relevant Abnormalities in ECG Evaluations (Safety Analysis Set)
CT-12.5 Listing of Potentially Clinically Relevant Abnormalities in ECG Evaluations (Safety Analysis Set)
CT-13.1 Summary of Mean Change From Baseline by Study Week in DIEPSS (Safety Analysis Set)
CT-13.2 Summary of Mean Change From Baseline by Study Week in AIMS Total Score and Item Scores 8, 9 and 10 (Safety Analysis Set)
CT-13.3 Summary of Mean Change From Baseline by Study Week in BARS, Global Clinical Assessment of Akathisia (Safety Analysis Set)
CT-14.1 Summary of Mean Change From Baseline by Study Week in Sheehan-STS Score (Safety Analysis Set)
CT-14.2 Summary of Mean Change From Baseline by Study Week in Sheehan-STS - Total Score (Safety Analysis Set)
CT-14.3 Summary of Mean Change From Baseline by Study Week in Sheehan-STS - Suicidal Ideation Subscale Score (Safety Analysis Set)
CT-14.4 Summary of Mean Change From Baseline by Study Week in Sheehan-STS - Suicidal Behavior Subscale Score (Safety Analysis Set)
CT-15.1 Summary of Mean Change From Baseline by Study Week in ADCS-ADL Total Score (Safety Analysis Set)
CT-15.2 Summary of Mean Change From Baseline by Study Week in MMSE Total Score (Safety Analysis Set)

Appendix 5

List of Subject Data Listings

AE-1	Adverse Events (Subjects Assigned to Treatment)
DEMOG-1	Demographic Characteristics (Subjects Assigned to Treatment)
DREAS-1	Discontinued Subjects and Reason for Discontinuation (Subjects Assigned to Treatment)
LAB-1	Laboratory Test Results: Serum Chemistry (Subjects Assigned to Treatment)
LAB-2	Laboratory Test Results: Hematology (Subjects Assigned to Treatment)
LAB-3	Laboratory Test Results: Urinalysis (Subjects Assigned to Treatment)
LAB-4	Laboratory Test Results: Other Laboratory Tests (Subjects Assigned to Treatment)
LAB-5	Pregnancy Test (Subjects Assigned to Treatment)
EFF-1	Cohen-Mansfield Agitation Inventory (CMAI) (Subjects Assigned to Treatment)
EFF-2	Clinical Global Impression - Severity of Illness (CGI-S) (Subjects Assigned to Treatment)
EFF-3	Clinical Global Impression - Improvement (CGI-I) (Subjects Assigned to Treatment)
PDATA-1.1	Inclusion and Exclusion Criteria (Subjects Assigned to Treatment)
PDATA-1.2	Inclusion and Exclusion Criteria (Screening Failures)
PDATA-2	Treatment Assignment List (Subjects Assigned to Treatment)
PDATA-3	Study Completion Status and Reasons for Discontinuation (Subjects Assigned to Treatment)
PDATA-4	Medical History (Subjects Assigned to Treatment)
PDATA-5	Alzheimer's Disease History (Subjects Assigned to Treatment)
PDATA-6	Patient Care (Subjects Assigned to Treatment)
PDATA-7.1	Prior and Concomitant Medications (Subjects Assigned to Treatment)
PDATA-7.2	Prior and Concomitant Therapy (Subjects Assigned to Treatment)
PDATA-8	Physical Examination (Subjects Assigned to Treatment)
PDATA-9	Vital Signs (Subjects Assigned to Treatment)
PDATA-10	Electrocardiogram Results (Subjects Assigned to Treatment)
PDATA-11.1	Sheehan-Suicidality Tracking Scale (S-STS) - Other than Q15 and Q16 (Subjects Assigned to Treatment)
PDATA-11.2	Sheehan-Suicidality Tracking Scale (S-STS) - Q15 (Subjects Assigned to Treatment)
PDATA-11.3	Sheehan-Suicidality Tracking Scale (S-STS) - Q16 (Subjects Assigned to Treatment)
PDATA-12	Drug-Induced Extrapyramidal Symptoms Scale (DIEPSS) (Subjects Assigned to Treatment)
PDATA-13	Barnes Akathisia Rating Scale (BARS) (Subjects Assigned to Treatment)
PDATA-14	Abnormal Involuntary Movement Scale (AIMS) (Subjects Assigned to Treatment)
PDATA-15	Mini-Mental State Examination (MMSE) (Subjects Assigned to Treatment)
PDATA-16	Alzheimer's Disease Cooperative Study - Activities of Daily Living (ADCS-ADL) (Subjects Assigned to Treatment)
PDATA-17	Post-treatment Follow-up (Subjects Assigned to Treatment)
PDATA-18	Screening Failures
PDEV-1	Major Protocol Deviations by Type of Deviation (Subjects Assigned to Treatment)
SMED-1	Study Medication Administration (Subjects Assigned to Treatment)
SMED-2	Study Medication Compliance (Subjects Assigned to Treatment)
SUBEX-1	Subjects Excluded From Analysis Set (Subjects Assigned to Treatment)
